# **13.5.** Safety and Tolerability Analyses

Safety will be evaluated based on the occurrence of AEs, vital signs, results of clinical laboratory tests, and ECG findings. Reported AE terms will be coded using the Medical Dictionary for Regulatory Activities (MedDRA®) version 21 preferred terms and system organ classes.

Treatment-emergent AEs (TEAEs) are defined as any AE that begins on or after the first administration of the study drug. Adverse event severity will be graded according to the CTCAE v5.0 and terms recorded on the CRFs will be mapped to preferred terms using the most recent version of the Medical Dictionary for Drug Regulatory Activities (MedDRA).

All AEs will be listed. The incidence of TEAEs will be summarized for each group and overall, by severity, and by relationship to study drug as assessed by the Investigator. The summary tables will include the number and percentage of patients with TEAEs overall, by system organ class, and by preferred terms within each system organ class. Similar tables will be prepared for SAEs, TEAEs leading to discontinuation, as well as additional categories of AEs as defined in the SAP.

Results of clinical laboratory tests will be summarized by visit for the absolute value and for change from baseline. Tables showing the shift from baseline will also be presented.

ECG findings will be listed.

Concomitant medications will be categorized and presented using the World Health Organization Anatomical Therapeutic Chemical (WHO-ATC) drug classification system.

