3.13.4. Clinical Laboratory Parameters

Laboratory parameters will be presented in conventional (ie, US) units. Only scheduled laboratory parameters, as specified in Table 1, will be included in the laboratory results summaries, unless specified otherwise. All laboratory data, including those collected at unscheduled visits, will be included in the listings.

For all quantitative parameters listed in Table 1, the actual value and the change from baseline to each postbaseline visit will be summarized by visit using descriptive statistics. Only data collected as scheduled will be included in the summaries. For each parameter, the mean (+/- SE) at each scheduled visit will be plotted for its actual value and its change from baseline. Data collected at the EOS/ET visit will be included as one time point regardless of subjects' EOS status.

In addition, where applicable, hematology and chemistry laboratory determinations will be categorized according to NCI CTCAE (version 5) grades and shifts from baseline NCI CTCAE grades to maximum and final post-baseline grades will be assessed. The baseline and final grades will be defined respectively as the grade of the last measurement collected prior to the first dose of study drug, and as the last post-baseline measurement collected no more than 30 days after the last dose of study drug.

The maximum NCI CTCAE toxicity grade value will be the value with the highest NCI CTCAE toxicity grade collected after the first dose of study drug and within 30 days following study drug discontinuation. In cases where multiple values are collected on the same day, the maximum grade value will be selected as the value for that day.

The number and percentage of patients with baseline grades versus maximum post-baseline grades of and baseline grades versus final post-baseline grades will be summarized.

Detailed listings of data for subjects experiencing NCI CTCAE grade \geq 3 hematology and chemistry values will be provided. All measurements collected, regardless of the number of days after study drug discontinuation will be included in these listings.

Pregnancy test data will be listed.

Number of subjects who meet protocol defined event of clinical interest criteria (Section 12.1.1 of protocol) as below will be summarized and corresponding listing will be presented.

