• An elevated aspartate aminotransferase or alanine aminotransferase laboratory value that is $\geq 3 \times$ the upper limit of normal (ULN) and an elevated total bilirubin laboratory value that is $\geq 2 \times$ ULN and an alkaline phosphatase laboratory value that is $< 2 \times$ ULN.

For urinalysis, the number of abnormalities at any post-baseline visit will be summarized.

Hematology	Chemistry	Urinalysis	Other
 Haematocrit Haemoglobin Red blood cell count (RBC) Total white blood cell count (WBC) Platelet count Differential blood count including: Basophils Eosinophils Neutrophils Lymphocyte Monocyte 	 Sodium Potassium Phosphorus Glucose Total protein BUN Serum creatinine CrCl Albumin Total bilirubin ALT AST LDH ALK-P CO₂ or bicarbonate^a Uric acid Calcium Chloride Magnesium Direct bilirubin, if total bilirubin is elevated above the upper limit of normal 	 Specific gravity Protein pH Glucose Ketones Blood Microscopic examination of sediment, only if urinalysis dipstick results are abnormal (2+ or higher) Urine pregnancy test^b 	 Serum β-hCGb PT (INR) aPTT TSH Cortisol (morning) ACTH

 Table 1:
 Clinical Laboratory Assessments

Abbreviations: ACTH=adrenocorticotropic hormone; ALK-P=alkaline phosphatase; ALT=alanine a minotransferase; ANC=absolute neutrophil count; a PTT=activated partial thromboplastin time; AST=aspartate aminotransferase; BUN=blood urea nitrogen; CBC=complete blood count; CO₂=carbon dioxide; CrCl=creatinine clearance; hCG=human chorionic gonadotropin; INR=international normalized ratio; LDH=lactic dehydrogenase;

PT=prothrombin time; TSH=thyroid-stimulating hormone.

a If considered standard of care in local region.

b Perform on women of childbearing potential

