3.13.6. Electrocardiograms (ECG)

ECG parameters (heart rate, RR interval, PR interval, QRS interval, QT interval will be summarized for each visit during the study. QT interval changes from baseline will also be descriptively summarized for each visit. The baseline value will be taken as the average of the triplicate ECG measurements taken prior to the first dose on Cycle 1 Day 1.

The number and percent of patients with abnormal ECG findings at any postbaseline visit will be summarized.

Individual ECG evaluation results will be provided in data listings. A supportive listing will present all values for a parameter for patients with abnormal ECG results.

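### The SAP's post-baseline counts of urinalysis and ECG abnormalities do not separate new from pre-existing findings, and its text omits the urinalysis shift table that the protocol promises

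*SAP*

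**What the plan says.** For ECG, SAP 3.13.6 states: "The number and percent of patients with abnormal ECG findings at any postbaseline visit will be summarized". The same section defines a baseline: "The baseline value will be taken as the average of the triplicate ECG measurements" taken before the first dose. It uses baseline for one interval: "QT interval changes from baseline will also be descriptively summarized for each visit". It also plans individual listings, including this one: "A supportive listing will present all values for a parameter for patients with abnormal ECG results".

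For urinalysis, SAP 3.13.4 states: "For urinalysis, the number of abnormalities at any post-baseline visit will be summarized". Earlier in that section, "For all quantitative parameters listed in Table 1, the actual value and the change from baseline to each postbaseline visit will be summarized", and Table 1 has a urinalysis column. The categorical shift analysis is narrower: "hematology and chemistry laboratory determinations will be categorized according to NCI CTCAE (version 5) grades and shifts from baseline NCI CTCAE grades" are assessed, with no mention of urinalysis.

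Protocol 13.5 says of clinical laboratory results, without exception: "Tables showing the shift from baseline will also be presented". The synopsis makes the same commitment. Protocol section 12 names urinalysis as one of the clinical laboratory parameters. For ECG findings, Protocol 13.5 plans a listing and nothing more.

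SAP section 5 declares no change to the protocol's statistical methods. The only revised definition in SAP 5.1 is that of the Efficacy Evaluable Population.

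**The concern.** Every patient receives the combination, and there is no reference therapy. A safety finding can therefore be judged only against the patient's own state before treatment. The SAP follows this principle almost everywhere else: CTCAE grade shifts for hematology and chemistry, a shift table for ECOG status (3.13.7), change from baseline for vital signs (3.13.5), and onset on or after first dose for adverse events (3.13.2). The ECG and urinalysis abnormality counts are the exceptions.

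Nothing in eligibility makes baseline abnormalities impossible. Exclusion criterion 17 bars serious arrhythmia and certain cardiac conditions, not an abnormal ECG as such. Protocol Table 3 has no urinalysis criterion. Repeated assessments give an old abnormality several chances to be seen again: footnote k of Protocol Table 4 asks for ECGs on three days of each cycle, and urinalysis continues after Cycle 4.

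At stake is whether these two summaries can be interpreted. As specified, they combine how common abnormalities already were in this pretreated population with how many appeared after dosing, and the reader cannot take the two apart.

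**Working it through.** **Step 1: the texts side by side.**

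| Item | Protocol | SAP | Result |
|---|---|---|---|
| Hematology, chemistry | Shift tables (13.5) | CTCAE grade shifts (3.13.4) | Consistent |
| Urinalysis | Shift tables (13.5, with section 12 defining scope) | Post-baseline abnormality count; no shift | Commitment not carried over; no change declared in SAP 5 or 5.1 |
| ECG findings | Listing (13.5) | Listings plus post-baseline patient count; no shift | More than the protocol asks, but baseline is ignored in the count |

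**Step 2: what the counts measure.** The documents state no figure to reproduce, so the following is for scale only. Let *b* be the proportion abnormal at baseline, *q* the chance that such an abnormality is seen again after baseline, and *e* the proportion of baseline-normal patients who become abnormal. None of the three is in the documents; all are assumptions. Baseline is taken as known for everyone, and the count is taken per patient.

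- Proportion reported = *bq* + (1 − *b*)*e*
- Newly abnormal, as a share of all patients = (1 − *b*)*e*
- Excess = *bq*, which is zero only if no baseline abnormality is seen again

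Example with *b* = 20%, *e* = 10%, *q* = 100%: reported = 0.20 × 1.00 + 0.80 × 0.10 = 0.28. Newly abnormal = 0.80 × 0.10 = 0.08. Pre-existing share of the count = 0.20 / 0.28 = 71%.

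With *e* = 10% throughout:

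| *b* | *q* | Reported | Newly abnormal (all patients) | Pre-existing share of count |
|---|---|---|---|---|
| 10% | 100% | 19.0% | 9.0% | 53% |
| 20% | 100% | 28.0% | 8.0% | 71% |
| 40% | 100% | 46.0% | 6.0% | 87% |
| 10% | 70% | 16.0% | 9.0% | 44% |
| 20% | 70% | 22.0% | 8.0% | 64% |
| 40% | 70% | 34.0% | 6.0% | 82% |

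Among patients normal at baseline, the newly abnormal proportion is *e* = 10% in every row. That is the quantity the proposed table would report, and it does not move with *b* or *q*. If *e* = 0 and *q* = 100%, the count reads 10%, 20% or 40% while nobody is newly abnormal. If *b* = 0, the count and the number newly abnormal are the same.

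**Step 3: whether other outputs fill the gap.** QT change from baseline does not show new rhythm or conduction findings. Change from baseline for quantitative parameters would reach urine pH and specific gravity, but does not clearly reach dipstick results such as protein, blood or ketones. The listings allow a new case to be traced patient by patient, but they are not a summary.

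**The case against.** A reader might infer that the SAP presents old abnormalities as if they had arisen on treatment, so that a harmless regimen would look toxic. The documents do not support that. The SAP calls both counts post-baseline; it does not call them new, treatment-emergent or drug-related. Treatment-emergent statements come from the adverse event tables (SAP 3.13.2). Under Protocol 12.1, a pre-existing condition enters those tables only if it worsens, and clinically significant out-of-range laboratory values are recorded as adverse events. A clinically significant new laboratory finding therefore has another route into the report.

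A reader might also infer that the ECG summary breaches the protocol. It does not: the protocol asks only for a listing, and the SAP gives more.

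Nor is it certain that urinalysis will be counted by abnormality rather than by patient. The sentence read alone suggests so, and such a figure would have no patient denominator. But the general rule in SAP 3.1 and section 7 is number and percentage of patients for categorical variables, and the sentence can be read with it. The mock tables are in a separate document and might settle this, or even show baseline status; they cannot be checked here.

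Lastly, the percentages above are assumed, and a worst post-baseline count by patient also accumulates with follow-up, so a shift table does not remove that feature.

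All of this limits the point. It does not answer the two observations that remain: the SAP text does not require either count to be related to baseline, and the urinalysis shift table is absent without being declared as a change.

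**Conclusion.** The point holds in a limited form. The planned urinalysis and ECG abnormality summaries cannot distinguish new from pre-existing findings in a study where baseline is the only comparator. For urinalysis this is also an undeclared departure from Protocol 13.5. For ECG it is a weakness that is cheap to remove, not a contradiction.

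The excess in the count equals the proportion of patients whose baseline abnormality is seen again: 10 to 40 percentage points for an assumed baseline prevalence of 10% to 40% with full persistence, and 7 to 28 points with 70% persistence (0.7 × 10% to 0.7 × 40%). These are illustrations, since the documents give neither prevalence nor persistence. The effect is confined to descriptive safety reporting; the primary efficacy analysis does not depend on these tables. The change should be made, but it is not critical to the trial's conclusions.

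**What to change.** In SAP 3.13.4, add a patient-level urinalysis shift table of baseline (normal, abnormal, missing) by worst post-baseline result, and express the existing count as number and percent of patients. This restores the table that the protocol commits to. If the sponsor prefers not to produce it, the omission should be declared in SAP section 5.

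In SAP 3.13.6, add the same table for the overall ECG finding. State how the pre-dose triplicates are classified as normal or abnormal, because the averaged baseline suits intervals but does not define a categorical finding.

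In both, report the number and percent newly abnormal among patients with a known normal baseline. Show patients with missing baseline separately; a denominator of all patients not abnormal at baseline would take them in and could count them as new cases.

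The cost is a few sentences of SAP text and two table shells. Baseline ECG and urinalysis are already scheduled in Protocol Table 4, so no new data are needed.

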3.13.7. Eastern Cooperative Oncology Group (ECOG) Performance Status

The ECOG Performance Status assesses the patients' activity status. Descriptions of activity status are presented in Table 2. Possible scores are 0 to 5. The number and percentage of patients with baseline score versus post-baseline scores will be summarized in a shift table. The data will be presented in the patient data listings.

Grade	Description
0	Normal activity. Fully active, able to carry on all pre-disease performance without restriction.
1	Symptoms, but ambulatory. Restricted in physically strenuous activity, but ambulatory and able to carry out work of a light or sedentary nature (eg, light housework, office work).
2	In bed <50% of the time. Ambulatory and capable of all self-care, but unable to carry out any work activities. Up and about more than 50% of waking hours.
3	In bed >50% of the time. Capable of only limited self-care, confined to bed or chair more than 50% of waking hours.
4	100% bedridden. Completely disabled. Cannot carry on any self-care. Totally confined to bed or chair.
5	Dead

 Table 2:
 Eastern Cooperative Oncology Group Performance Status

4. INTERIMANALYSES

No interim analyses are planned for this study.

5. CHANGES IN CONDUCT OR PLANNED ANALYSES FROM THE PROTOCOL

There are no changes made to the statistical methods specified in the ION-01-ALKS 4230 study protocol (dated 29 Dec 2018).

5.1. Revisions and/or clarification of definitions in SAP

Protocol Definition	SAP definition
Efficay Evaluable Population All patients who received at least 1 dose of both study drugs	Efficacy Evaluable Population All patients who received at least 1 dose of both study drugs and have minimum of one post-baseline scan

6. DEFINITIONS AND CONVENTIONS FOR HANDLING OF THE DATA

Dataset specifications will be provided in a separate document.

6.1. Analysis Visit Windows

Scheduled analysis visits are visits at scheduled timepoints as specified in the protocol (Table 1 Schedule of Assessments and Study Visits).

Scheduled analysis visits during the study period will be the same as the nominal visits collected in the eCRF. There will be one valid value of assessment kept for each scheduled analysis visit in summary/analysis statistics.

In the event that a patient chooses to withdraw from the study, the Investigator should make a reasonable effort to ascertain the reason(s) for withdrawal, while fully respecting the patient's rights. Enrolled patients are to be asked to return to the clinic for an End of Treatment (EOT) Visit. The EOT Visit should be scheduled as close as possible to the patient's last dose, and early termination assessments will follow the assessments scheduled to be conducted at the EOT Visit.

Unscheduled visits are visits with data collected outside of scheduled time points. Unscheduled visits will not be used for by-visit summary/analysis statistics, unless specified otherwise.

All unscheduled visits as collected in the eCRF will be included in listings.

Visit Day is calculated as (date of visit) – (date of the first dose of study drug) +1 day.

6.2. Efficacy Data Handling

The Censoring Rules for Overall Survival, Progression Free Survival and Duration of Response are defined according to the FDA guidance²

6.2.1 Censoring Rules for Overall Survival (OS)

The overall survival censoring date for a patient is listed in Table 3. The start date is the first dose date of the study drug.

Situation	Date of Death or Censoring	Outcome
Death during study	Date of death	Death
Patient still alive at data cut-off/death occurred after data cut-off	Date of cut-off	Censored
Patient lost to follow-up	Date last known to be	Censored
before data cut-off	alive	

Table 3:Censoring Rules for Overall Survival (OS)

6.2.1. Censoring Rules for Duration of Response (DOR)

The Duration of Response censoring dates for a patient is in Table 4. The Start date: the date of first documentation of response (CR or PR).

Table 4:	Censoring Rules for Duration of Response
----------	---

Situation	Date of Progression or Censoring	Outcome
No baseline or unreadable baseline assessment, but readable post-baseline assessments	Date of the 1 st dose of the study drug	Censored
Progression documented between scheduled visits	 Earliest of Date of radiological assessment showing new lesion (if progression is based on new lesion); or Date of last radiological assessment of measured lesions (if progression is based on increase in sum of measured lesions) 	Progressed
Death before first PD assessment	Date of death	Progressed
Death between adequate assessment visits	Date of death	Progressed
Treatment discontinuation for undocumented progression	Date of last tumor assessment with no documented progression	Censored
Treatment discontinuation for toxicity of other reason	Date of last tumor assessment with no documented progression	Censored
Patients still on treatment without PD as of data cut-off	Date of last tumor assessment	Censored
Treatment discontinuation for other than PD or death with post-baseline tumor assessments	Date of last tumor assessment	Censored
New anticancer treatment started before PD or death	Date of last tumor assessment before start of new treatment	Censored
Death or PD after two or more missed tumor assessments	Date of the last tumor assessment before missed assessments	Censored
Only NE assessments after CR, PR, SD	Date of last tumor assessment before NE assessments	Censored

6.2.2. Censoring Rules for Progression Free Survival (PFS)

The Progression Free Survival censoring dates for a patient is listed in Table 5. The start date is the first dose date of the study drug.

Table 5:	Censoring Rules for Progression Free Survival
----------	---

Situation	Date of Progression or Censoring	Outcome
No baseline or unreadable baseline assessment, but readable post-baseline assessments	Date of the 1 st dose of the study drug	Censored
Progression documented between scheduled visits	 Earliest of Date of radiological assessment showing new lesion (if progression is based on new lesion); or Date of last radiological assessment of measured lesions (if progression is based on increase in sum of measured lesions) 	Progressed
Death before first PD assessment	Date of death	Progressed
Death between adequate assessment visits	Date of death	Progressed
Treatment discontinuation for undocumented progression	Date of last tumor assessment with no documented progression	Censored
Treatment discontinuation for toxicity of other reason	Date of last tumor assessment with no documented progression	Censored
Patients still on treatment without PD as of data cut-off	Date of last tumor a ssessment	Censored
Treatment discontinuation for other than PD or death with post-baseline tumor assessments	Date of last tumor assessment	Censored
New anticancer treatment started before PD or death	Date of last tumor assessment before start of new treatment	Censored
Death or PD after two or more missed tumor assessments	Date of the last tumor assessment before missed assessments	Censored
Only NE assessments after CR, PR, SD	Date of last tumor assessment before NE assessments	Censored

6.3. Safety Data Handling

All effort should be made to obtain missing information from the Investigator. For vital signs, laboratory testing (chemistry, hematology, urinalysis), and 12-lead ECGs, only observed data will be used for analyses, and missing data will not be imputed.

6.4. Handling of Partial Dates of Concomitant Medication

Partial start dates of prior and concomitant medication will be assumed to be the earliest possible date consistent with the partial date. Partial stop dates of prior and concomitant medications will be assumed to be the latest possible date consistent with the partial date. In the case of completely missing stop date, medication will be assumed to be ongoing.

For summaries of prior medications, if an incomplete start date is collected for a medication, the medication will be assumed to be a concomitant medication unless there is evidence that confirms that the medication was not a concomitant medication (eg, the medication end date is prior to the first dose of study drug)

If both the start and end date of medication are missing, then these will be excluded from summary statistics but included in the patient data listings.

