- f Prior medications Record all medications taken within 30 days of Screening Visit. Concomitant medications Enter new medications started within 28 days before the first dose of study drug through the Safety Follow-up Visit. Record all medications taken for AEs.
- g AEs and laboratory safety measurements will be graded per NCI CTCAE v5.0. All AEs, whether gradable by CTCAE or not, will also be evaluated for seriousness. The Week 3 AE review can be captured via telephone; no visit is required.
- h Record all AEs occurring within 30 days after the last dose of study drug. Report all SAEs (related and unrelated to study drug) and ECIs occurring up until 90 days after the last dose of study drug or 30 days after the start of new anticancer treatment, whichever comes first. Afterwards, report only SAEs and ECIs that are related to study drug.
- i Vital signs include temperature, pulse, respiratory rate, weight, and blood pressure. Height will be measured at Visit 1 only.
- j ECOG Performance Status and laboratory tests for screening are to be performed within 10 days prior to the first dose of study drug.
- k ECGs should be performed on Day 1, Day 3, and Day 5 of each cycle. ECGs should be performed in triplicate approximately 5 minutes apart at each time point assessed. ECGs will be obtained predose of pembrolizumab on Cycle 2 Day 1. ECGs should also be obtained predose of ALKS 4230, at the end of infusion, and 1 hour (±15 minutes) after the completion of administration of ALKS 4230.
-  A pregnancy test (urine or serum) must be given to all women of childbearing potential before each treatment cycle begins. Pregnancy test results must be confirmed as negative before Dose 1 of each cycle is administered for all cycles.
- m Coagulation factors (PT/INR and aPTT) should be tested as part of the screening procedures and before collection of the post-treatment (second) biopsy for all patients. Any patient receiving anticoagulant therapy should have coagulation factors monitored closely throughout the study.
- n After Cycle 1, laboratory samples can be collected up to 72 hours prior to Day 1 (CBC with differential; complete serum chemistry panel, including magnesium, calcium, and phosphorus; and urinalysis). CBC and complete serum chemistry panel should also be done up to 72 hours prior to Day 1 of the ALKS 4230 infusion.

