3.9. Prior and Concomitant Medications

A prior medication is defined as any medication taken with an end date prior to the first dose of study drug. A prior regimen can contain more than one prior medications. A concomitant medication is defined as any medication (1) that started before the first dose of study drug and was continuing at the time of the first dose of study drug, or (2) started on or after the date of the first dose of study drug and continued up to 30 days after the patient's last dose of study drug.

The number and percentage of patients who have taken prior or concomitant medications will be summarized using the WHO-ATC generic drug name dictionary (version: March 2016 or higher) for the Safety population.

For the summary table, if a subject has taken a concomitant medication more than once, the subject will be counted only once for that medication. A patient who reports the use of two or more medications with same start date will be counted only once in the summary of "Any Concomitant Medication." Similar rules will apply to prior medications as well.

The concomitant medication will be reviewed by medical team to identify the anti-cancer therapy treatment during the study.

All reported medications (including prior medications and concomitant medication) will be included in listing.

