Progression-free survival (PFS) is defined as the time from the first dose to the first documentation of objective tumor progression, start of alternate therapy or death due to any cause. Patients who do not have disease progression or have not died will be censored at the last known time that the patient was progression free. If a patient begins a new anticancer treatment (either systemic or local) prior to documented progression or death, or if a patient is removed from the study due to undocumented clinical disease progression, then the patient will be censored at the last assessment where the patient was documented as progression free prior to the intervention. Patients with 2 or more consecutive missing response assessments prior to a visit with documented progression (or death) will be censored at the last date of tumor assessment when the patient was documented to be progression free. The detailed censoring rules for PFS is in section 6.2.2.

Progression-free survival will be calculated as follows (in weeks):

(date of disease progression/death – first dose date +1)/7

The survival distribution of PFS will be estimated using Kaplan-Meier methodology. The median PFS will be provided along with the two-sided 95% CIs based on the Efficacy Evaluable population. In addition, Kaplan-Meier curves will be provided. The 6-month PFS rate will be estimated using the Kaplan-Meier estimate.

• Time to Progression:

Time to progression (TTP) is defined as the time from the first dose to the confirmed tumor progression. All events of disease progression will be included regardless of whether the patient discontinued the study drug. If the patient has not experienced disease progression, the patient's data will be censored at the date of last disease assessment. Data for patients without any disease assessments performed after the first dose will be censored at the date of first study drug.

The TTP will be calculated as follows (in weeks):

(date of disease progression – date of first dose + 1)/7

TTP will be analyzed by Kaplan-Meier methodology. Median TTP will be calculated and 95% confidence interval for median TTP will be presented.

• Overall Survival:

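### The earliest-day rule for partial medication dates can place new anticancer therapy before the progression that preceded it, turning documented PFS and DOR events into earlier censorings

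*SAP*

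**What the plan says.** Three parts of the SAP bear on this point.

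- **Identification (SAP 3.9).** "The concomitant medication will be reviewed by medical team to identify the anti-cancer therapy treatment during the study". The SAP states no other route. Its definition of a concomitant medication ends with drugs that "continued up to 30 days after the" last dose. Protocol Table 4, footnote f, sets collection in similar terms: "Enter new medications started within 28 days before the first dose of study drug through the Safety Follow-up Visit".
- **Dating (SAP 6.4).** "Partial start dates of prior and concomitant medication will be assumed to be the earliest possible date consistent with the partial date". This is the SAP's only partial-date rule for medications. It has no exception for anticancer therapy and no check against the PD date or the last study dose.
- **Use (SAP 6.2, Tables 4 and 5).** For the situation "New anticancer treatment started before PD or death", the patient is censored at "Date of last tumor assessment before start of new treatment". The row is the same for DOR and PFS. The PFS text in SAP 3.11.3 agrees and includes local therapy: "If a patient begins a new anticancer treatment (either systemic or local) prior to documented progression or death".

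SAP 3.11.3 also defines the end of PFS as "first documentation of objective tumor progression, start of alternate therapy or death due to any cause". That makes new therapy an event, whereas Table 5 makes it a reason to censor.

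**The concern.** Patients who progress often move to another treatment, and a start date recorded only by month is a common data problem. The earliest-day convention is reasonable for sorting medications into prior and concomitant. It is a poor choice for deciding whether a therapy came before or after PD, because it always pushes the therapy back in time.

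For a patient who truly switched after PD, the error runs in one direction under Tables 4 and 5: the documented event is removed and follow-up is cut back to an earlier scan. Median DOR, median PFS and the 6-month PFS rate would then look better than the data support. There is no control arm in which the same error would offset it.

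**Working it through.** The documents give no figure for this effect, so there is none to reproduce. The check applies the stated rules and counts how often they misorder PD and therapy.

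**1. One dated patient (constructed).** First dose 2 Sep 2019; scans without PD on 14 Oct and 25 Nov; PD on 6 Jan 2020; new therapy on 20 Jan, recorded as January 2020.

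- SAP 6.4 imputes 1 Jan 2020, which is before 6 Jan, so the new-therapy row of Table 5 applies.
- True PFS: (126 + 1)/7 = 127/7 = 18.1 weeks, event.
- PFS as derived: (84 + 1)/7 = 85/7 = 12.1 weeks, censored on 25 Nov.

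**2. How often a missing day misorders the dates.** Let PD fall on day d of a 30-day month, d uniform on 1 to 30, with therapy g days later. The imputed date is strictly before PD when therapy falls in the same month (d + g ≤ 30) and PD is not on the 1st (d ≥ 2). The share is (29 − g)/30, or zero if negative.

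| Gap g (days) | Calculation | Share |
|---|---|---|
| 7 | 22/30 | 73% |
| 14 | 15/30 | 50% |
| 21 | 8/30 | 27% |
| 28 | 1/30 | 3% |
| 35 | none | 0% |

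Counting every actual PD date from 1 Mar 2019 to 28 Feb 2021 gives 74%, 51%, 28%, 5% and 0%. With day and month both missing, the shares are 98% at 7 days and 92% at 28 days.

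**3. Which gaps the SAP window catches.** After the first on-study scan, scans fall within 7 days before every second cycle (protocol Table 4, footnote s), about Days 15 to 21 of the preceding cycle. If the last ALKS 4230 dose was on Day 5 and treatment stops at that PD, the 30-day window closes near Day 35. That is 35 − 21 = 14 to 35 − 15 = 20 days after PD. Therapy found in that setting has the short gaps at which misordering is most likely.

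**4. Overall size (illustration).** Assumptions: median PFS 12 weeks, scans every 6 weeks, 60% of progressors start captured therapy 7 to 28 days after PD (uniform), and only the day is missing when a date is partial. The mean of (29 − g)/30 over g = 7 to 28 is 11.5/30 = 0.383. The share of PFS events lost is therefore about 0.6 × 0.383 × p = 0.23p, where p is the share of partial dates. A Kaplan-Meier simulation agrees:

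| p | PFS events censored | 6-month PFS, true to derived |
|---|---|---|
| 5% | 1.2% | 25.0% to 25.3% |
| 10% | 2.3% | 25.0% to 25.7% |
| 20% | 4.7% | 24.9% to 26.3% |
| 50% | 11.8% | 25.1% to 28.9% |

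The value of p is not in the documents. The 50% row is there to show the range, not as an expectation.

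**The case against.** **The link is inferred.** SAP 6.4 follows the safety data section, the rest of its text is about classifying and summarizing medications, and neither it nor Tables 4 and 5 cites the other. The dataset and programming specifications are separate documents and may handle these dates differently. This stands as a caution. Even so, the SAP offers no other rule, and a programmer following it would use this one.

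**Capture is limited.** Collection ends at the Safety Follow-up Visit, which protocol Table 5 allows before new therapy starts. Much next-line therapy may never reach SAP 6.4. This stands and reduces the number of patients affected. It does not help those who are captured, whose gaps tend to be short.

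**Gaps may be long.** Protocol Table 7 has first PD rechecked at about 4 to 6 weeks, and stable patients may stay on study drug meanwhile. For patients who wait, a missing day rarely or never crosses PD. This stands too; the effect falls mainly on patients who switch sooner.

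**Direction for PFS.** Under the SAP 3.11.3 wording that counts alternate therapy as an event, an early imputed date moves the PFS event earlier and shortens PFS. The upward bias in PFS therefore holds only if Table 5 prevails. DOR has no such conflict.

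**Stronger readings.** A reader might infer that all therapy begun after PD is dated before it. The rules do not do that: the start date must be partial, PD must fall later in the same unknown month or year, and the therapy must be captured. Nor is sharing a calendar month enough. That count gives 77%, 53%, 30% and 7% for gaps of 7 to 28 days, but it includes PD on the 1st, where the two dates tie. The year-only case looks severe, but when first dose and PD fall in the same year, 1 January precedes the first study dose and should be noticed in review.

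**Conclusion.** The point holds in conditional form. The SAP's stated rules, applied together, can replace a documented progression with an earlier censoring, biasing DOR, and PFS under Table 5, upward. For an affected date the risk is substantial at short gaps: half of day-missing dates at 14 days.

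The overall effect is probably small. It is about 2% to 5% of PFS events and 0.7 to 1.4 percentage points on the 6-month rate if 10% to 20% of start dates lack the day. Those figures rest on the assumed partial-date share, median, scan interval and gaps listed in the working.

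The documents do not support reading this as a threat to the trial's main conclusion. The objective improvement rate and OS do not use the rule. TTP as defined in SAP 3.11.3 has no new-therapy censoring, so it gives a partial check: a patient with a TTP event but PFS censored for new therapy should be queried. The change is worth making before database lock because it is cheap and the present rule gives a wrong result where it applies.

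**What to change.** 1. Exempt new anticancer therapy from SAP 6.4 for PFS and DOR, and say so in SAP 6.2.
2. Impute a partial start date within the recorded period (month or year), but not before a PD documented in that period. If the imputed start and PD tie, count the PD as the event. Cap the date at the end of the period: PD on 30 June with therapy recorded as June gives 30 June, not 1 July.
3. For systemic therapy only, also apply a floor at the day after the last study dose, subject to the same cap. The floor does not suit local therapy, because protocol 8.4.2 may allow some radiotherapy on study.
4. Use any new-therapy start dates already recorded in follow-up, not only those in the concomitant-medication window. The documents do not show how completely these are recorded.
5. Add a sensitivity analysis of PFS and DOR with the earliest-date imputation.
6. Reconcile the PFS definition in SAP 3.11.3 with the new-therapy row of Table 5, so that new therapy is either an event or a censoring, not both.

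In the dated example, the imputed start can be no earlier than 6 Jan 2020, and the PFS event at 18.1 weeks is kept. For therapy truly begun after PD, misordering by this route falls to 0% at every gap.

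The cost is a few SAP sentences, one derivation and one extra analysis, using data already held. The downside is that a patient who truly switched before PD in the same unknown period would be counted as an event. The sensitivity analysis shows how much that could matter.
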